**MODIFICATION HISTORY**

Unique Identifier for Version	Author	Date of iAP Version	Changes from the Previous Version
1.0	PPD	2022-11-10	Initial version

# 1 INTRODUCTION

This document presents the Integrated Analysis Plan (IAP) for the study MS202559\_0001.

The IAP is written to reflect the content of the study protocol (v2.0, 2022-10-21).

The objective of the IAP is to describe the data analysis methodology and the way the study results will be presented for the final analysis that informs the clinical investigation report.

[figure not shown]
## 1.1 OBJECTIVES AND OUTCOMES

	Objective	Outcome	IAP section
OBJECTIVES (PRIMARY)	
 
1. To describe the distribution of sensor collected data on physical activity, heart rate, heart rate variability, temperature, respiration rate, cough frequency, and sleep pattern, by severity of COPD exacerbations.
 
	Primary Outcome: COPD exacerbations Sensor data 
 
○ physical activity
 
○ (resting) heart rate
 
○ heart rate variability
 
○ temperature
 
○ respiration rate
 
○ ratio of in- vs. expiration time
 
○ cough frequency
 
○ sleep pattern
 
	3.4.4.1
OBJECTIVES (SECONDARY)	
 
2. To predict moderate or severe COPD exacerbations by building a statistical model employing sensor-derived data and demographic and medical covariates.
 
3. To evaluate the correlation of sensor collected data with           
 
a) patients' self-assessed health status and symptoms (CAT) at baseline and study end,
 
b) lung function and lab values at baseline and study end,
 
c) and with history of mild, moderate, and severe exacerbations at study end.
 
 
 
4. To investigate whether changes in physical activity, heart rate, heart rate variability, temperature, respiration rate, cough frequency, and sleep pattern in the 3-month
 
	Secondary Outcome: Health status by CAT questionnaire summary score Lung function by plethysmography Laboratory values Number of COPD exacerbations per type  Secondary Outcome: Health status by CAT questionnaire summary score	3.4.4.2 3.4.4.3 3.4.4.4

observation period, are associated with changes of the patient self-assessed symptoms (CAT).

5. To predict the CAT score and changes thereof by building a statistical model employing sensor-derived data and demographic and medical covariates.

Health status by CAT questionnaire 3.4.4.5 summary score

[figure not shown]

#### STUDY TIME FRAME

#### **COPD Cohort**

Participants will be enrolled consecutively, during regular scheduled clinical visits. The Baseline visit (Day 0) marks the index date and can take place once the participant has provided written informed consent to participate in the study. Enrolled COPD participants will be followed for a 3-month observation period (until End of Study visit) or until premature discontinuation from study, whichever occurs first. A look back period of 3 years is used to determine prior history of COPD exacerbations.

Figure 1 Study design overview

### Participants in the calibration Cohort

Participants in the calibration cohort will be enrolled in an internal medicine center in Germany. The Baseline visit (Day 0) can take place once the participants provided written consent to participate in the study and marks the index date. Participants in the calibration cohort will be followed for a 2-week observation period.

## 1.3 STUDY POPULATION

### 1.3.1 Study Population, Eligibility criteria, Inclusion Criteria

The Study population consists of a COPD cohort and a calibration cohort. The COPD cohort comprises participants with COPD stage II-IV and a corresponding medical history of up to 3 years. Participants in the calibration cohort will be enrolled in an internal medicine center in Germany.

The study population will be identified according to the below inclusion and exclusion criteria. For inclusion in the study, all of the following inclusion criteria must be fulfilled:

For COPD participants:

1. Participants capable of giving signed informed consent, as described in Section 10.1 of the protocol, which includes compliance with the requirements and restrictions listed in the ICF and this protocol
2. Participants  $\geq 40$  and  $\leq 80$  years at baseline
3. Diagnosis of COPD stage II to IV (documented post-bronchodilator FEV1/FVC  $< 0.7$  and FEV1  $< 80\%$  predicted)
4. History of moderate or severe exacerbations ( $\geq 2$  moderate exacerbations or  $\geq 1$  severe exacerbations in any 12-month time window during last 3 years prior to inclusion, considering that last 12 months may reflect lower exacerbation rate due to Covid-19 measures)

For participants in the calibration cohort:

1. Participants capable of giving signed informed consent to participate, as described in Section 10.1 of the protocol, which includes compliance with the requirements and restrictions listed in the ICF and this protocol
- 2.
3. Participants  $\geq 40$  and  $\leq 80$  years at baseline

Participants are not eligible for this study if they fulfill any of the following exclusion criteria:

For COPD participants:

1. Participants who, at the discretion of the Investigator, are unlikely to complete the study or will not be able to provide reliable information for the study
2. Clinically relevant and/or serious concurrent medical conditions including, but not limited to visual problems, severe mental illness or cognitive impairment, musculoskeletal or movement disorders, cardiac disease (e.g., heart failure, arrhythmia [esp. atrial fibrillation and conduction blocks]), lung cancer (currently treated) that in the opinion of the Investigator, would interfere with participant's ability to participate in the study or draw meaningful conclusions from the study
3. Participants with a cardiac pacemaker, defibrillators, or other implanted electronic devices
4. Participants with known allergies or sensitivity to silicon or hydrogel
5. Less than 6 weeks since previous moderate/severe exacerbation

For participants in the calibration cohort:

1. Participants who, at the discretion of the Investigator, are unlikely to complete the study or will not be able to provide reliable information for the study
2. Clinically relevant and/or serious concurrent medical conditions including, but not limited to visual problems, severe mental illness or cognitive impairment, musculo-skeletal or movement disorders, cardiac disease (e.g., heart failure, arrhythmia [esp. atrial fibrillation and conduction blocks]), lung cancer (currently treated) that in the opinion of the Investigator, would interfere with participant's ability to participate in the study or draw meaningful conclusions from the study
3. Participants with a cardiac pacemaker, defibrillators, or other implanted electronic devices
4. Participants with known allergies or sensitivity to silicon or hydrogel
5. Diagnosis of pulmonary disease including, but not limited to COPD, asthma, pulmonary fibrosis, with impact on the lung function and exercise capacity

### 1.3.2 Study size

Sample size calculation is based on the second part of the primary objective, especially on predicting exacerbations of a severe or moderate type as outcome.

Assuming a desirable sensitivity and specificity of 0.85 for our algorithm and requiring that the lower 95% confidence limit should be at least 0.50 (with a probability of 0.95) for this exploratory approach, the number of observed exacerbation events needed is 18 (1).

Assuming that COPD patients within our eligibility criteria (GOLD stage II-IV with a history of at least 2 moderate to severe exacerbations within any 12 month period within the last 3 years and at least 1 exacerbation within the last 12 months) show a frequency of 2 moderate or severe exacerbations per year, COPD participants will have 0.5 events in 3 months (the in-study time). Further assuming that event occurrence over 3 months for every individual participant follows a Poisson distribution with parameter  $\lambda = 0.5$ , the number of events in the overall study population is also Poisson distributed and the corresponding parameter is the sum of individual parameters  $\lambda$ . Calculations show that a  $\lambda$  of 30 is needed to reach an upper cumulative distribution probability of 0.99 for observing at least 18 exacerbations. Therefore, 60 participants are needed to observe at least 18 exacerbation events within the 3-month observation period.

The events of interest in the context of the present study are COPD exacerbations (severe or moderate), exactly the onset of an exacerbation. For building the binary classifier predictive models we also require “no exacerbation” events. We will sample such events randomly from periods with no exacerbations, avoiding 2 weeks before and after an exacerbation.

Considering a drop-out rate of 10%, the estimated number is 67 COPD participants that need to be included in this study.

This recruitment number is also in good agreement with published studies with regards to the ability to build predictive models for exacerbations. Studies with similar recruitment numbers (2) have been able to predict exacerbations based on single parameters studied. Strong features can compensate for low numbers in COPD machine learning model building as shown in (3), and using several features improves the accuracy of predictive models as seen in Jensen 2012.

The study will also observe 10 participants in a calibration cohort for a limited time (2 weeks). This calibration cohort is intended to obtain sensor parameter ranges for individuals who are not suffering from COPD or other pulmonary diseases. These parameter ranges will be used to calculate distance measures of parameters (e.g., physical activity) for COPD patients, and obtain additional sensitivity measures for the sensors used with regards to distinguishing COPD symptoms from a calibration population. The number of participants for these secondary objectives is chosen on an exploratory basis, no sample size calculation has been conducted here. Since we expect no major perturbations (e.g., exacerbations) within the calibration population, we deem a time period of 2 weeks sufficient for generating a representative sample of the participants sensor data.

## 2 VARIABLES

### 2.1 VARIABLE DEFINITIONS

#### 2.1.1 Sociodemographic

- Demographics data at baseline: sex, age at Baseline visit, height, and weight, race and ethnicity, age at COPD diagnosis (date of COPD diagnosis - date of birth / 365.25)

- Body mass index (BMI [ $\text{kg}/\text{m}^2$ ]) will be calculated based on height and weight:
  - $\text{BMI} = \text{weight} [\text{kg}] / (\text{height} [\text{cm}]/100)^2$
- Smoking status/history: cigarette usage (never, current, former), cigar usage (never, current, former), pipe usage (never, current, former), e-cigarette usage (never, current, former), water pipe usage (never, current, former), chewing tobacco (never, current, former); *frequency per day/week/month/year will also be considered within each category*

### 2.1.2 Medical/Medication history, comorbidities, vital signs

- Medical history at baseline
- Comorbidities at baseline
- Current medication including COPD treatment at baseline
- Date of diagnosis of COPD
- COPD severity (GOLD stage) at baseline
- Number of moderate or severe exacerbations prior to baseline visit (preceding 36 months, in case available)
- Physical examination/vital signs
  - Systolic Blood Pressure
  - Diastolic Blood Pressure
  - Pulse
  - Temperature
  - Respiration Rate

### 2.1.3 Lung function and laboratory values

The following variables will be measured at baseline, at each exacerbation visit, and at end of study visit.

- Current or last available body plethysmography parameters:
  - FEV1 [L],
  - FVC [L] (forced vital capacity),
  - FEV1/FVC [],
  - TLC [L] (total lung capacity),
  - RV [L] (residual volume),
  - FRCpleth [L] (functional residual capacity),
  - IC [L] (inspiratory capacity),

- Raw [kPa s L-1] (=ratio of sRaw to FRCpleth; airway resistance),
- sRaw [kPa s] (specific airway resistance),
- TV [L] (mean tidal volume),
- ERV [L] (expiratory reserve volume),
- IRV [L] (inspiratory reserve volume)
- Blood gas analysis:
  - (capillary) pO2 [mmHg]
  - O2 saturation [%]
  - pCO2 [mmHg]
- Serum CRP [mg/l] and serum procalcitonin levels [ng/ml]
- Blood count (CBC with differential):
  - Hb [g/dL]
  - Hct [%]
  - Erythrocyte count [ $10^6/\mu\text{L}$ ]
  - MCV [fL]
  - MCH [pg]
  - MCHC [g/dL]
  - Reticulocytes [ $\times 10^3/\mu\text{L}$ ] [% (of erythrocytes)]
  - RDW []
  - platelet count [ $10^3/\mu\text{L}$ ]
  - WBC count [ $\times 10^3/\mu\text{L}$ ]
  - Lymphocytes [ $\times 10^3/\mu\text{L}$ ] [%]
  - Monocytes [ $\times 10^3/\mu\text{L}$ ] [%]
  - Neutrophils [ $\times 10^3/\mu\text{L}$ ] [%]
  - Eosinophils [ $\times 10^3/\mu\text{L}$ ] [%]
  - Basophils [ $\times 10^3/\mu\text{L}$ ] [%]

#### 2.1.4 Sensor measurements by Vivalink wearable device and ePRO diary

Unless indicated otherwise, the following variables are measured continuously throughout the observation period.

- Physical activity including stair climbing, (calculated based on continuous accelerometer measurement) [daily average] (derived parameter)

- Heart rate as beats per minute [daily average]
- Resting heart rate (resting state as determined by accelerometer, beats per minute) [daily average] (derived parameter)
- Heart rate variability reflecting differences in time intervals between 2 R-waves in the ECG (milliseconds) [daily average] of the following parameters:
  - SDRR (standard deviation of RR intervals),
  - SDNN (standard deviation of NN intervals),
  - SDNNI (Mean of the standard deviations of all the NN intervals for each 5 min segment of a 24 h HRV recording),
  - RMSSD (Root Mean Sum of Squared Distance),
  - ln(RMSSD) (natural logarithm of RMSSD),
  - pNN50 (percentage of successive RR intervals that differ by more than 50 ms)
  - SI (stress index),
  - LF power (low frequency fraction of HRV, 0.04 – 0.15 Hz),
  - HF power (high frequency portion of HRV, 0.15 – 0.40 Hz),
  - LF/HF (ratio of LF-to-HF power) (derived parameter)
- Temperature [daily average, minimum and maximum values] (derived parameter)
- Respiration rate (breath per minute) [daily average, minimum and maximum values]
- Ratio of in- vs expiration time [daily average, minimum and maximum values] (derived parameter)
- Cough frequency (derived parameter, count per day)
- Sleep pattern (derived parameter, hours of sleep)
- Self-reported activities as collected by the participant app, logged as activity per time-stamp, allowing for several logs of the same activity per day:
  - coughing,
  - coughing with sputum production,
  - spray use,
  - non-scheduled spray use,
  - eating,
  - going to bed,
  - waking up,
  - walking,
  - climbing stairs,
  - and physical exercise

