During the Baseline visit each enrolled participant will be provided with a Vivalink wearable device and a connected phone and trained on the how to use these devices. The participants should wear the Vivalink device continuously, day and night (except for charging times and situations described in the instructions for use), during the observation period to ensure recording of ECG, accelerometer, and temperature data.

A study digital application is installed on the phone provided with the Vivalink wearable device for the participants to fill in the CAT questionnaire, label activities or events relevant for the interpretation of sensor signals, receive notifications/reminders and visualize their progress with study related activities.

The CAT questionnaire will be filled in by each participant at home, once per day, every day during the observation period electronically using the study digital application. The validated translation of the CAT questionnaire in German will be incorporated as an electronic questionnaire in the software application for the study participants. The participants will be trained during the baseline visit how to use the study application to fill in the CAT questionnaire.

The study digital application will be used also for the labeling of activities relevant for interpretation of data collected with the wearable device. The application will contain a predefined list of options: coughing, coughing with sputum production, spray use, non-scheduled spray use, eating, going to bed, waking up, walking, climbing stairs, and physical exercise that can be easily selected to indicate when such an event/activity occurs. The participants will be trained to use the application to correctly label events and activities. Participants will be requested to label at least 5 events per day, every day during the observation period.

The digital study application will also provide participants automated notifications/reminders related to the Vivalink device (e.g. to charge or to wear the device), to fill in the CAT questionnaire, and to input labeling information. Participants will be encouraged to fulfill these daily tasks by reminders and notifications triggered once data is not entered as requested. A dashboard with compliance data will be provided to the participants allowing them to have an overview of outstanding tasks and their performance to fill out questionnaires, wear the device, and label events to encourage them to be compliant.

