9.9 Limitations of the Research Methods

- The data is collected from a very limited number of study sites in Germany. Hence the study population may not be representative of the population of patients with COPD. In addition, the fact that participation in the study requires cognitive capabilities to use applications and devices used for data collection in the study may cause selection bias towards a younger age group.
- Daily averages will be calculated to represent continuous measurements each day. There may be additional information encoded in smaller time periods (hour by hour or minute by minute) data or through defining bouts of activity.
- Some of the outcomes are based on subjective self-assessment e.g. COPD symptoms and health status will be assessed by the CAT score. In validation studies, the CAT score has been shown to be a valid and reliable tool to assess perceived health status (Jones 2013), though validity of the online version remains to be proven.
- The number of observed exacerbations will be low, and predictive models will need to be refined and validated in a larger population.

- Severe and moderate AECOPDs will likely be encountered in only ~40% of the participants with COPD. This may impact the generalizability of predictive models for AECOPDs.
- This study is a national study in Germany and will only recruit patients with sufficient proficiency in the German language. It is therefore impossible to assess potential bias in the gathered data and conclusions with regards to language, ethnicity, cultural background, country of origin, and social factors not encountered in the study population. This refers both to PROs and the interpretation of sensor data. Future studies will need to study these potential biases in a multinational setting.
- Mild exacerbations are captured via the labelling section in the patient facing application as “additional medication used” (self-reporting). Therefore, the capture of mild exacerbations depends on patients’ adherence to the intended application use and daily reporting. Mild exacerbations may therefore be under-reported (but also over-reported in case of erroneous entries).
- Participants may not adhere to the intended constant wearing or charging regimens of the device and therefore available data may have too many gaps to allow meaningful interpretation.

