#### 3.4.3 Derived variables

Variable	Original data	Description of derived data	Algorithm to develop/Detail for implementation
Body mass index (BMI [kg/m^2])	Measured height and weight. (Demographics data at baseline)	Weight (kg) / (Height [cm]/100) 	NA

Physical activity, including stair climbing	Continuous accelerometer measurement, self-reported activities	Classification algorithm, similar to the one described in (5)	An activity flag is extracted from the accelerometer by Vivalink, by using a predefined threshold for adult movement. For stair climbing, first periodic movement must be determined, by using frequency analysis on specific time windows, and generating a ratio to the total spectrum indicating periodic activity over a certain threshold (See (5) for more details). Climbing of stairs is determined by a classification algorithm, here a tree classifier and a nearest neighbors classifier will be tested, using the activity labels inputted by the patient for supervised learning.
Heart rate	ECG	Beats per minute.	Heart rate is provided by Vivalink. In case it needs to be calculated (e.g., for initial comparison of results obtained), the process to follow is to use the heartpy python package, by using the 'process' method. See (6) for details on how to use the package. Said method returns two datasets, one of them being the measures, where one can extract the beats per minute (bpm).  <code>working_data, measures = heartpy.process(ecg_data, ecg_fs)</code> <code>Heart_Rate= measures['bpm']</code> Where ecg_fs is the sample rate of the ECG, 128 in this case.
Resting heart rate	Accelerometer, ECG	Resting state as determined by accelerometer, Beats per minute extracted from ECG	The resting heart rate is calculated as described in the heart rate calculation, but is calculated only in periods where the activity flag is 0.

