Frequency of additional medication	Self-reported activities	Self-reported use of additional medication	Count of the number of times the use of additional medication (Bedarfsmedikament) as a log activity is reported per day.

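### Cough is a raw count per day with no worn-time denominator, so partly worn days, always including Day 0, read low without being flagged

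*SAP*

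**What the plan says.** **Cough.** SAP 2.1.4 lists "Cough frequency (derived parameter, count per day". The derivation in SAP 3.4.3 covers filtering, features and classifiers but no exposure time.

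**Activity.** SAP 2.1.4 has "Physical activity including stair climbing, (calculated based on continuous accelerometer measurement) [daily average] (derived parameter", and SAP 3.4.3 adds: "An activity flag is extracted from the accelerometer by Vivalink, by using a predefined threshold for adult movement". The hours that enter the average, and the treatment of an unworn patch, are not stated.

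**Reliever use.** SAP 3.4.3: "Count of the number of times the use of additional medication (Bedarfsmedikament) as a log activity is reported per day". SAP 3.4.5.1 lists it among the Objective 1 parameters.

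**Expected wear and app use.** Protocol 9.1.1: "The participants should wear the Vivalink device continuously, day and night (except for charging times and situations described in the instructions for use". For the app: "Participants will be requested to label at least 5 events per day, every day during the observation period". Protocol 9.9 concedes: "Participants may not adhere to the intended constant wearing or charging regimens of the device and therefore available data may have too many gaps".

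**Missing data.** SAP 3.4.4 leaves missing daily values unimputed in descriptive analyses and allows imputation for machine learning. SAP 3.4.6 reruns the models on variables that are no more than 20% missing.

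**Where the values are used.** SAP 3.4.5.1 tabulates them at Day 0, over Days 8 to 14, and in windows around exacerbations. SAP 3.4.5.2 names cough and activity among the model inputs. SAP 3.4.5.3 correlates sensor data, cough included, with CAT, lung function and laboratory values at Day 0 and End of Study.

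**The concern.** A count per day is proportional to the hours in which events can be detected. Two days with the same cough rate but different worn hours give different counts, and the shorter day looks healthier. That day holds a number rather than a gap, so rules for missing values never reach it.

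On visit days this follows from the schedule alone. On Day 0 the count depends partly on the time of the appointment. In Objective 1 that makes the Day 0 column not comparable with the others. In Objective 3 it adds noise unrelated to disease to the correlations.

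Around exacerbations the problem is conditional. If participants wear the patch less when unwell, the windows compared in Objective 1 differ in exposure as well as in physiology, and a real rise in cough is reduced, hidden or reversed. Cough is also an Objective 2 input, so the same distortion would reach the classifier.

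**Working it through.** The plan gives no figure for worn hours, valid days or completeness of app logging, so there is nothing of its own to reproduce. All hours below are assumptions, used to show a range.

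**1. Do existing rules catch a partly worn day?**
- SAP 3.4.4 acts on missing values; a half-worn day has a value.
- SAP 3.4.6 filters whole variables, not days.
- The gap and 70% rules in SAP 2.3.1 only define mild exacerbations.
- The reminders and compliance dashboard (Protocol 9.1.1), withdrawal for unreliable data (9.2.5) and data-quality monitoring (9.7.3) act during conduct and adjust no daily value.

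So none of them does.

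**2. Day 0, with no adherence assumption.** The patch is handed out at the visit. Taking a calendar day and assumed fitting times of 09:00 and 15:00, the hours left are 24 − 9 = 15 and 24 − 15 = 9. At the same cough rate the counts differ by 15/9 = 1.67-fold. The End of Study day is cut short in the same way when the patch is returned at the visit.

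**3. Cough around an exacerbation, if wear falls.** Observed ratio = true rate ratio × (worn hours near the event / usual worn hours), with usual wear assumed to be 22 h. The true rise that would be exactly hidden is 22/worn hours − 1.

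| Worn hours near event | Rate unchanged | True 1.3-fold | True 1.5-fold | Rise exactly hidden |
|---|---|---|---|---|
| 20 | 20/22 = 0.91 | 1.18 | 1.36 | 10% |
| 16 | 16/22 = 0.73 | 0.95 | 1.09 | 37.5% |
| 12 | 12/22 = 0.55 | 0.71 | 0.82 | 83% |

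Coughs per worn hour return 1.00, 1.30 and 1.50 in every row, provided the worn hours are representative of the day.

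**4. Activity.** Assume 16 h awake at level 1.0 and 8 h asleep at 0.1. The full-wear average is (16 × 1.0 + 8 × 0.1)/24 = 0.70.
- Half the waking hours unworn: counting non-wear as zero gives (8 + 0.8)/24 = 0.367, or 0.52 of the full-wear value. Averaging over worn time gives 8.8/16 = 0.55, or 0.79.
- Night unworn: counting non-wear as zero gives 16/24 = 0.667, or 0.95. Averaging over worn time gives 16/16 = 1.00, or 1.43.

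The direction depends on the unstated denominator and on which hours are missed.

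**5. Reliever use.** Observed ratio = true ratio × share of uses logged, with full logging at baseline. For a true rise from 2 to 4 uses per day, 50% logged shows 4 × 0.5 = 2 (ratio 1.0), and 25% logged shows 4 × 0.25 = 1 (ratio 0.5).

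**The case against.** The strongest reply is that most of the harm depends on adherence falling during an exacerbation, and no passage says or quantifies that. This stands: every wear figure above is assumed, and the exacerbation bias can only be put conditionally.

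Several stronger readings are tempting, but the documents do not support them:
- **That a day without app entries counts as zero reliever use.** No passage says so. SAP 3.4.4 names labelling information among the daily variables that can be missing. What is absent is a rule for telling zero from missing.
- **That logging reliever use is optional because only five labels a day are requested.** The request is a minimum. Protocol Table 4 says app labelling supplies the medication data used to identify mild exacerbations, and 9.9 refers to intended daily reporting.
- **That activity is uncorrected and an unworn patch reads as inactive.** Activity is a daily average. If it is taken over worn time it is already scaled for duration, and the vendor's off-body handling is not described in the available text.
- **That Day 0 distorts every change from baseline.** Protocol 9.3 uses Days 8 to 14 as the sensor baseline for change. Day 0 matters for its own Objective 1 column and for Objective 3.
- **That hospital non-wear will drive the Objective 2 classifier.** Protocol Section 7 bases prediction on data preceding the exacerbation, while in-hospital non-wear falls mainly at or after onset.

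The reminders, dashboard and monitoring should reduce gaps, the study is declared exploratory, and 9.9 discloses the limitation. The contents of the table plan and the device instructions are not available here, so an adherence table cannot be ruled out. Such a table would describe wear without correcting the counts. None of this answers the cough definition or the partial visit days.

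**Conclusion.** The point holds for cough. As written, the SAP produces a daily count that is too low on any partly worn day and has no rule to detect it. On Day 0 this is certain. On the End of Study day it holds when the patch is returned at the visit. Around exacerbations the size depends on wear that the documents do not report: under an assumed 22 h falling to between 20 and 12 h, the count is 9% to 45% low at an unchanged cough rate. This assumes coughs are spread evenly over worn hours.

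For activity and reliever use the finding is narrower: the averaging denominator and non-wear handling, and the zero-versus-missing rule, are unstated. A reader might infer that activity will show a false fall near exacerbations; the bias could go either way.

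Confidence is moderate. This is a cheap improvement to the SAP and does not call the design into question.

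**What to change.** Amend SAP 2.1.4 and 3.4.3:

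1. Define worn time from usable ECG contact.
2. Replace the daily cough count with coughs per worn hour, day and night separately.
3. Average activity over worn time only. This corrects for duration but not for which hours were missed (the 1.43 in the unworn-night example).
4. Set daily sensor values to missing below a pre-set minimum worn time, with one alternative cut-off as a sensitivity analysis.
5. Set the reliever count to missing on days with no app entry at all. This does not correct partial logging, which should be acknowledged.
6. Show median worn hours and the number of app-use days beside each Objective 1 window.

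The cost is SAP wording and some programming on data already collected. The downside is fewer analysable days. Many Day 0 values will fall below any demanding minimum, so the Day 0 column in Objective 1 and the Day 0 correlations in Objective 3 will thin out. The cut-off should be fixed before the data are analysed.
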